21.2. Data Quality Assurance

Accuracy and reliability of the clinical study data will be ensured by selection of qualified investigators, and appropriate study centers, review of protocol procedures with the investigators and associated personnel prior to the study, and by periodic monitoring visits by the sponsor. CRFs will be reviewed for accuracy and completeness by the sponsor during on site monitoring visits and after their return to the sponsor, and any discrepancies will be resolved with the investigator or designees, as appropriate.

21.3. Record Retention

All clinical sites will maintain all records pertaining to this study for a minimum of two years after marketing approval or formal discontinuation of investigational product development. The Sponsor will notify the clinical sites of the date of discontinuation. No study-related records, written or electronic, will be destroyed or transferred without specific written approval by the Sponsor.

22.0 PUBLICATION POLICY

The CTA mutually signed by the Investigator(s) and Tusker Medical, Inc., defines and describes the nature of the study agreement.

The Sponsor retains the rights to this protocol and the CRFs before and after data entry. Tusker Medical, Inc. reserves the right to review any reports of this study to verify that the information is accurate and to ensure the content and timing of any such publication is mutually agreed upon by the Investigator(s) and Tusker Medical, Inc. Draft abstracts, manuscripts, and materials for presentation at scientific meetings should be provided to the sponsor at least 30 working days prior to submission.

Clinical trial information will be registered in the clinical trial registry databank maintained by the National Institutes of Health/National Library of Medicine (NIH/NLM) per FDAAA 801 requirements. If a future publication results from this study, authorship will be established according to ICMJE guidelines.

1.0 Scope

This is the Statistical Analysis Plan (SAP) for the final analysis of data collected under Protocol Number CPR007001.

2.0 Trial Objectives

The primary objective is to confirm safety and effectiveness (procedural success and tube placement tolerability) of tympanostomy tube placement using the TULA Iontophoresis and Tube Delivery Systems for children in an in-office procedure.

The trial will also evaluate anesthesia effectiveness, tube patency and tube retention.

3.0 Trial Endpoints

3.1 Co-Primary Endpoints

- **Procedural Success:** Proportion of subjects in the pivotal cohort with successful placement of Tusker Medical tympanostomy tubes in all indicated ears in an office procedure.
- **Tube Placement Tolerability:** Mean subject-reported pain score following TDS tube placement using the Faces Pain Scale-Revised (pivotal cohort children ages 5 and older)

3.2 Safety Endpoint

Occurrence of adverse events, by subject.

3.3 Secondary Efficacy Endpoints

Tube Patency: Tube Patency is the proportion of subjects in the pivotal cohort, in which a Tusker Medical tube was successfully placed, with functionally patent tube(s) in all successfully treated ears at the 3-week post-procedure follow-up visit.

Tube Retention: Tube Retention is the proportion of subjects in the pivotal cohort, in which a Tusker Medical tube(s) was successfully placed, with presence of a Tusker Medical tube across the TM in all successfully treated ears at the 3-week post-procedure follow-up visit.

Anesthesia Effectiveness: Proportion of subjects in the pivotal cohort, who completed iontophoresis in all indicated ears, with adequate anesthesia for TT placement in all treated ears as determined by physician's evaluation of TM anesthesia prior to tube placement.

CPR007004 Rev E
Effective 11/29/2017

Page 4 of 26

[REDACTED]

Term	Percentage
GMOs	95
Organic	92
Natural	90
Artificial	20
GMOs	95
Organic	92
Natural	90
Artificial	20
GMOs	95
Organic	92
Natural	90
Artificial	20

Three horizontal black bars of varying lengths are positioned side-by-side. The top bar is the longest, the middle bar is slightly shorter, and the bottom bar is the shortest.

[REDACTED]

[REDACTED]

[REDACTED]

[REDACTED]

For more information, contact the Office of the Vice President for Research and Economic Development at [contact] or [contact].

A series of five horizontal black bars of varying lengths, decreasing from left to right. The first bar is the longest, followed by a shorter one, then a very long one, another short one, and the shortest bar on the far right.

[REDACTED]

[REDACTED]

[REDACTED]

[REDACTED]

[REDACTED]

[REDACTED]

4.0 Trial Design

This study is a prospective, single-arm, multicenter evaluation of safety and effectiveness of iontophoresis using the IPS and TDS for TT placement in-office for children indicated for tympanostomy tube placement.

The study consists of OR lead-in, in-office lead-in and pivotal cohort subjects. [REDACTED]

[REDACTED] Study enrollment and procedures will occur in two stages.

Stage 1 (OR Lead-In Cohort): Stage 1 consists of tube placement procedures in the OR under general anesthesia. [REDACTED] each investigator will enroll 2 lead-in subjects in the operating room (OR) undergoing tube placement using the Tube Delivery System to place the tympanostomy tube(s) under general anesthesia (ie, no lidocaine iontophoresis). Stage 1 is comprised of the OR Lead-In Cohort up to 100 subjects).

Stage 2 (In-Office Lead-In Cohort and Pivotal Cohort): Stage 2 consists of in-office procedures using both the lidocaine Iontophoresis System and the Tube Delivery System for the in-office tube placement procedure, including both the Office Lead-In Cohort and the Pivotal Cohort. [REDACTED]

[REDACTED] each investigator will enroll 2 lead-in subjects in-office undergoing tube placement using the TDS with local anesthesia facilitated by the Iontophoresis System (up to 100 subjects in the Lead-In Office Cohort). Investigators may enroll into the Pivotal Cohort following completion of their lead-in office procedures. The pivotal cohort will include 222 children (ages 6 months through 12 years, inclusive) with evaluable data indicated for tympanostomy tube placement enrolled at up to 25 investigational centers (minimum of 15 centers).¹ The pivotal phase will include 102 children ages 5 years and older, and 120 children with evaluable data less than 5 years of age.

4.1 Design of the Pivotal Phase

The pivotal phase of the study aims to confirm safety, and determine whether the in-office tube placement procedure achieves an acceptable procedural success rate and acceptable tube placement tolerability as established by performance goals. The pivotal cohort will consist of a sample of 222 children including 102 children age 5 through 12 years old, and 120 children less than 5 years of age.

¹ Subjects who are consented for the study will be considered enrolled. Throughout the protocol and SAP, enrollment numbers will reflect consented enrolled subjects with evaluable data per SAP.

The study includes two primary endpoints. The first primary endpoint, Procedural Success, will be the proportion of pivotal cohort subjects with Tusker Medical tympanostomy tubes placed in all indicated ears in an office procedure. The statistical test for the Procedural Success primary endpoint is a hypothesis test against a procedural success performance goal. The second primary endpoint, Tube Placement Tolerability, will be the mean subject-reported pain score following TDS tube placement using the Faces Pain Scale-Revised (FPS-R) (pivotal cohort children ages 5 and older only). The statistical test for the Tube Placement Tolerability primary endpoint is a hypothesis test against a Tube Placement Tolerability performance goal.

[REDACTED]

[REDACTED] The study design thus employs a Bayesian hierarchical gatekeeper strategy whereby a successful first test will permit the trial to continue to the second statistical test. The test against the Procedural Success performance goal occurs in two steps:

1) The initial test against the performance goal is conducted on the older children in the pivotal cohort, once the study has accrued evaluable data for 102 children ages 5 through 12 years of age. [REDACTED]

[REDACTED] The older child group will be tested against the procedural success primary performance goal using a Bayesian hierarchical algorithm designed to borrow information from the enrolled younger children as appropriate given the performance results at the time of the first test. [REDACTED]

[REDACTED] If the older group achieves the performance goal, the second test is applied as in step 2.

2) Once the younger group achieves 120 evaluable subjects, they may be tested against the Procedural Success performance goal. The 102 older (5-12 years old) children are included in the Bayesian hierarchical model used to evaluate the younger subjects against the performance goal.

The second primary endpoint, Tube Placement Tolerability, will be tested for the older group only at step 1, above, at time of the initial test for Procedural Success for the 102 older children.

[REDACTED]

5.0 Study Cohorts

5.1 Lead-In OR Cohort

The Lead-In OR Cohort will consist of all children who underwent a lead-in procedure in the OR. The Lead-In OR Cohort safety and effectiveness data will be analyzed and presented separately.

5.2 Lead-in Office Cohort

The Lead-In Office Cohort will consist of all children who underwent a lead-in procedure in-office. The Lead-In Office Cohort safety and effectiveness data will be analyzed and presented separately.

5.3 Pivotal Cohort

The Pivotal Cohort will consist of children who underwent an in-office procedure using the TULA System (not including Lead-In subjects). The Pivotal Cohort safety and effectiveness data will be analyzed and presented separately.

6.0 Analysis Sets

The following analysis sets are defined for the Pivotal Cohort.

6.1 Full Analysis Set (FAS)

All subjects in whom lidocaine is introduced into the ear canal and for whom iontophoresis was initiated will be included in the FAS.

6.2 Per Protocol

The Per Protocol Set is a subset of the FAS and includes all FAS subjects without major protocol deviations. Major protocol deviations include:

- Eligibility violations
- Procedural deviations with the potential to affect anesthesia efficacy (eg, abbreviation of iontophoresis or use of incorrect local anesthesia drug).

6.3 Safety Analysis Set

The Safety Analysis Set will include all pivotal cohort subjects in which the lidocaine solution is introduced into the ear canal.

7.0 Subject Disposition

Subject disposition will be summarized with counts and percentages. Categories summarized will include the number of subjects who signed informed consent, number of screen failures (with reasons), and the number enrolled, completed, and discontinued, as well as reasons for discontinuation. The summary of disposition will also include the number and percentage of subjects included in each analysis set described in Section 6, and for each age strata and cohort.

8.0 Demographic Characteristics and Medical History

Demographic characteristics including age, sex and race/ethnicity will be descriptively summarized for all enrolled subjects in each of the defined study cohorts. Significant medical history will also be summarized for all enrolled subjects in each of the defined study cohorts. Demographic characteristics and medical history will be presented separately for each of the Analysis Sets defined for the Pivotal Cohort, and for each age strata.

[REDACTED]

[REDACTED]

[REDACTED]

10.0 Primary Endpoint Analyses

10.1 Procedural Success

There are two primary endpoints for the study. The first primary efficacy endpoint is Procedural Success defined as the proportion of subjects in the pivotal cohort FAS achieving procedural success evaluated against a performance goal of 68%.

If both ears of a subject are indicated for TT placement, the procedure must be successful in both ears for the procedure to be counted as a success on a subject-level for the Procedural Success primary efficacy endpoint. If either ear does not receive a tube, the procedure is not considered a success. If a subject requires only a unilateral tube, the procedure is considered a success when the indicated ear has received the tube. The procedural success definition is aligned with the desired clinical outcome; the child has Tusker tubes placed in all indicated ears while avoiding general anesthesia and an OR visit. The statistical test for the pivotal cohort procedural success primary endpoint is a Bayesian hypothesis test against a procedural success performance goal.

- 1) The initial test against the performance goal is conducted on the older children in the pivotal cohort, once the study has accrued evaluable data for 102 children ages 5 through 12 years of age.

The primary hypothesis is

Test 1:

$H_0: p_{5+} \leq 68\%$ vs. $H_a: p_{5+} > 68\%$,

where p_{5+} is the proportion of subjects 5 through 12 years old achieving procedural success.

This hypothesis will be tested using a Bayesian hierarchical model evaluating whether the posterior probability of H_a is at least 0.975, which is analogous to a classical hypothesis test at the 0.025 significance level in the FAS comprising only subjects 5 through 12 years old. This Bayesian analysis applies the test to the older group, while borrowing data from all enrolled evaluable subjects less than 5 years old, as appropriate given the performance results at the time of the first test. [REDACTED]

[REDACTED] If the older group achieves the performance goal, the second test is applied as described in step 2. Procedural success will also be summarized in the Per Protocol set comprising subjects 5 through 12 years of age.

2) Once the younger group achieves 120 evaluable subjects, they may be tested against the Procedural Success performance goal. The second test evaluates the younger subjects against the performance goal while borrowing data from the 102 older subjects using a Bayesian hierarchical model as appropriate given the performance of the older group.

Test 2:

$H_0: p_{<5} \leq 68\%$ vs. $H_a: p_{<5} > 68\%$,

where $p_{<5}$ is the proportion of subjects in the younger group (6 months through <5 years old) achieving procedural success.

Test 2 is also performed using a Bayesian hierarchical model, requiring a 97.5% posterior probability of H_a . [REDACTED]

[REDACTED]

[REDACTED]

[REDACTED]

[figure not shown]
[REDACTED]

10.2 Tube Placement Tolerability

The second primary endpoint is Tube Placement Tolerability defined as mean subject-reported pain score following TDS tube placement using the Faces Pain Scale-Revised (FPS-R) (pivotal cohort children ages 5 and older only).

If both ears of a subject are indicated for tympanostomy tube placement, the tube placement pain score is collected after the second ear tube placement is completed (one tube placement pain score per subject). The FPS-R score will be collected after any manipulations required to place the tube so that the pain score fully reflects the activities required to place the tube. [REDACTED]

The mean pain score for subjects in the pivotal cohort FAS, for whom tube placement was successful, will be evaluated against a performance goal of 4.2 pain score.

The test against the performance goal is conducted on only the older children in the pivotal cohort, once the study has accrued evaluable data for 102 children ages 5 through 12 years of age.

The statistical test for the Tube Placement Tolerability primary endpoint is a hypothesis test against a Tube Placement Tolerability performance goal. [REDACTED]

[REDACTED] Only completers, ie, subjects with FPS-R scores after successful tube insertion in all indicated ears, will be included in the primary analysis.

The primary hypothesis is

$$H_0: p_{5+} \geq 4.2$$

vs.

$$H_a: p_{5+} < 4.2$$

Where p_{5+} is the mean Tube Placement FPS-R for subjects 5 through 12 years old.

This hypothesis will be tested using a standard classical t-test at the 0.025 significance level in the FAS comprising only subjects 5 through 12 years old. [REDACTED]

[REDACTED]

[REDACTED]

[REDACTED]

11.0 Secondary Endpoint Analyses

[REDACTED]

[REDACTED]

[REDACTED]

[REDACTED]

[REDACTED] The secondary endpoints (Tube Patency, Tube Retention and Anesthesia Effectiveness) are functions of the tube and iontophoresis device performance and are not anticipated to vary by subject age. Therefore, the second test on the full (pooled) pivotal cohort is appropriate.

11.1 Tube Patency

Tube Patency is the proportion of subjects in the pivotal cohort FAS, in which a Tusker Medical tube was successfully placed, with functionally patent tubes in all successfully treated ears at the 3-week post-procedure follow-up visit.

The statistical test for the pivotal cohort Tube Patency secondary endpoint is a hypothesis test for the proportion of subjects with functional tube patency at the 3-week follow-up visit against a Tube Patency performance goal. The mid-P^{2,3,4} method for a single proportion will be used to test

$$H_0: p \leq 80\% \text{ vs. } H_a: p > 80\%$$

This endpoint will be considered met if the p-value from the test is less than 0.025.

² Berry G, Armitage P. Mid-p confidence intervals, a brief review. *The Statistician*, 1995; 44:417-423.

³ Lynderup S, Laake P. Power comparison of two-sided exact tests for association in 2x2 contingency tables using standard, mid p, and randomized test version. *Statistics in Medicine*, 2003; 22:3859-3871.

⁴ Lancaster HO. Significance tests in discrete distributions. *JASA*, 1961; 56:223-234.

11.2 Tube Retention

Tube Retention is the proportion of subjects in the pivotal cohort FAS, in which a Tusker Medical tube was successfully placed, with presence of a Tusker Medical tube across the tympanic membrane in all successfully treated ears at the 3-week post-procedure follow-up visit.

The statistical test for the pivotal cohort Tube Retention secondary endpoint is a hypothesis test for the proportion of subjects with a Tusker tube at the 3-week follow-up visit against a Tube Retention performance goal. A mid-P method for a single proportion will be used to test

$H_0: p \leq 88\%$ vs. $H_a: p > 88\%$

This endpoint will be considered met if the p-value from the test is less than 0.025.

[REDACTED]
[REDACTED]

[REDACTED]
[REDACTED]

[REDACTED]
[REDACTED]
[REDACTED]

[REDACTED]
[REDACTED]
[REDACTED]
[REDACTED]
[REDACTED]

[REDACTED]
[REDACTED]

[REDACTED]
[REDACTED]
[REDACTED]

[REDACTED]
[REDACTED]
[REDACTED]

[REDACTED]
[REDACTED]

[REDACTED]

[REDACTED]

[REDACTED]

[REDACTED]

[REDACTED]

[REDACTED]

[REDACTED]

[REDACTED]

[REDACTED]

14.0 Safety Endpoint Analyses

14.1 Adverse Events

Adverse events (AEs) reported during the study will be coded using the Medical Dictionary for Regulatory Activities (MedDRA). The number and percentage of subjects reporting adverse events will be summarized by MedDRA system organ class and preferred term by cohort and in total.

The study will present the totality of safety data, by subject including:

- Serious device, procedure, and drug-related events
- Other serious events
- Non-serious device, procedure, drug-related events
- Other non-serious events

For all AE tables, a subject reporting the same AE more than once will be counted once when calculating the number and percentage of subjects with that particular event. If a subject reports the same AE more than once or has the same AE on multiple occasions, the maximum severity grade recorded for the event will be presented.

Overall summaries of serious and non-serious AEs will be presented. The overall summaries will include the number and percentage of subjects experiencing AEs classified by treatment, relationship to device/procedure/study drug, MedDRA SOC (System Organ Class) and preferred term. Summaries of AEs will also be presented by severity for each treatment group including the number and percentage of subjects experiencing AEs classified by relationship to device/procedure/study drug, SOC and preferred term.

[REDACTED]

[REDACTED]

[REDACTED]

Safety data will be presented separately as follows:

- Lead-In OR Cohort
- Lead-In Office Cohort
- Pivotal Cohort

Complete subject listings of all AEs will be provided. For each AE the following will be specified: start and stop dates, severity grade, MedDRA SOC, relationship to study device, relationship to procedure, relationship to study drug, action taken, outcome of the adverse event and seriousness. Any unanticipated adverse events will be noted.

14.2 Erythema Assessment at Return Electrode Location

Erythema observed for the skin under the return electrode will be categorized by grade level (0 through 4) prior to and immediately after iontophoresis. Erythema findings will be summarized by number and proportion of subjects in the Safety Analysis Set for each erythema grade level for each Cohort. Number and proportion of subjects reporting discomfort at the return electrode location will be summarized.

14.3 Audiometric Assessments

Change in audiometric measurements (shifts) from baseline to the 3-week follow-up visit for subjects in the Safety Analysis Set will be presented using descriptive statistics (mean, SD, median, minimum and maximum). Shifts in air conduction (AC) and bone conduction (BC) hearing thresholds will be reported for each frequency (500, 1000, 2000 and 4000 Hz, and air conduction only at 8000Hz) and for each Cohort on a by-ear basis (treatment ears only). Shifts from baseline to each follow-up visit in air-bone gap (air conduction minus bone conduction) will also be reported for each frequency (500, 1000, 2000 and 4000 Hz) for each Cohort on a by-ear basis. Shifts in air conduction pure tone average (AC PTA), bone conduction PTA (BCA) and air-bone gap averages will be presented for each follow-up time point for each Cohort. For all PTA measurements, the PTA will be calculated by adding the threshold levels in decibels (dB) obtained at each frequency tested divided by number of frequencies tested.

Shift tables for air conduction pure tone averages greater than 15 dB (>15dB) by ear will be calculated, and presented for each Cohort for each follow-up time point.

Degree of hearing loss severity will be defined according to the protocol (slight through profound) and presented by subject for each Cohort and by relationship to study device, procedure or study drug.

Due to the differences in audiometric requirements for children dependent on age, all audiometry results will be presented by subjects less than 4 years of age, greater than 4 years of age, and overall.

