11.4.6. Audiometry

Audiometry will be employed to evaluate hearing status in each ear at screening (within 28 days prior to procedure) and at the 3-week post-procedure follow-up visit for all subjects age 4 years or older. Threshold testing will be conducted using air conduction and bone conduction at a minimum of 500, 1000, 2000 and 4000 Hz, and air conduction only at 8000Hz. Study sites will make efforts to measure hearing thresholds at all 5 frequencies. For younger subjects (less than 4 years of age), clinical study sites will attempt to collect audiometry at screening at a minimum of two frequencies for both air conduction (AC) and bone conduction (BC). The clinical study site audiologist will determine the most appropriate test method for each subject (visual reinforcement audiometry (VRA), conditioned play audiometry (CPA) or conventional audiometry). The method used at screening will be used for all follow-up assessments.

Audiometry is considered standard of care for this patient population and may be obtained prior to study informed consent as a screening assessment within 28 days prior to procedure.

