Possible	A clinical event, including laboratory test abnormality, with a reasonable time sequence to procedure, device or drug administration/exposure, but which could also be explained by concurrent disease, other interventions or drugs.
Not Related	A clinical event, including laboratory test abnormality, with a temporal relationship to procedure, device or drug administration/exposure which makes a causal relationship improbable, and in which concurrent disease, other interventions, other drugs or chemicals provide plausible explanations. A Not Related event may also not have a reasonable temporal relationship to procedure, device or drug administration/exposure.

*Causality definitions derived from WHO-UMC Causality Assessment Scale⁶⁸

Adverse Event Criteria – Hearing Loss

Audiometry will be used to assess changes to hearing thresholds for all ears. Investigators will diagnose post-treatment hearing impairment/loss if audiometry indicates a greater than 15-decibel (dB) change (worsening) in air conduction pure tone average for either ear. Classification of the level of hearing loss/impairment will be according to the American Academy of Audiology Childhood Screening Guidelines, as outlined in **Table 8**.^{69,70}

Table 8. Table of Hearing Threshold Change (Worsening) Classification

Level	Threshold Change
Slight	16-25 dB
Mild	26-40 dB
Moderate	41-55 dB
Moderately Severe	56-70 dB
Severe	71-90 dB
Profound	91 dB or greater

[figure not shown]

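### SAP 14.3 averages air conduction over five frequencies and bone conduction over four, so the >15 dB table can miss a 500–4000 Hz worsening of up to 18.75 dB when 8000 Hz is unchanged

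*SAP*

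**What the plan says.** SAP 14.3 gives one rule for every PTA: "the PTA will be calculated by adding the threshold levels in decibels (dB) obtained at each frequency tested divided by number of frequencies tested". Protocol 11.4.6 tests "air conduction and bone conduction at a minimum of 500, 1000, 2000 and 4000 Hz, and air conduction only at 8000Hz", and SAP 14.3 reports the same set. The full set is an aim for sites: "Study sites will make efforts to measure hearing thresholds at all 5 frequencies". For children under 4, sites attempt as few as two frequencies at screening.

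Three outputs depend on these averages or relate to them:

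- SAP 14.3: "Shifts in air conduction pure tone average (AC PTA), bone conduction PTA (BCA) and air-bone gap averages will be presented".
- SAP 14.3: "Shift tables for air conduction pure tone averages greater than 15 dB (>15dB) by ear will be calculated".
- Protocol 12.4: investigators diagnose hearing loss on a "greater than 15-decibel (dB) change (worsening) in air conduction pure tone average for either ear". It names no frequencies for the average. Table 8 then grades the change, starting at 16–25 dB (slight).

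SAP 14.3 also reports air- and bone-conduction shifts at each frequency by ear, with minimum and maximum. It reports the air-bone gap at each of 500, 1000, 2000 and 4000 Hz. SAP 21.0 lists all case report form data by subject.

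**The concern.** On the SAP's formula, the air and bone averages for the same fully tested ear cover different frequency sets. This does not depend on missed tests; it happens when every planned frequency is measured at both visits.

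What is at stake is the count of ears with hearing worsening. The 15 dB cut-off appears in both the adverse event criterion and the shift table, but only the SAP says how the average is built. If an investigator averages the four frequencies shared by air and bone conduction, an ear can be diagnosed with hearing loss yet be absent from the shift table. The protocol requires only one post-procedure audiogram, at 3 weeks, so no later required test would settle the difference.

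Two related matters arise from the same paragraph. A loss at 8000 Hz alone is heavily diluted in the average. And the average air-bone gap has no stated construction, although one possible construction would mix the two frequency sets.

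**Working it through.** The plan states no computed figure here to reproduce; 15 dB is a criterion.

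**Inputs.** Air-conduction frequencies on a complete audiogram: 5. Bone-conduction frequencies: 4 (Protocol 11.4.6, SAP 14.3). Cut-off: more than 15 dB (SAP 14.3, Protocol 12.4). The change at 8000 Hz, d8, is not given in the documents; it is an assumption, shown from −20 dB (improvement) to +20 dB (worsening).

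**1. The shift table.** Let x be the mean air-conduction worsening over 500–4000 Hz.

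Air-conduction PTA shift = (4x + d8)/5.

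The ear is not flagged when (4x + d8)/5 ≤ 15, that is when x ≤ (75 − d8)/4.

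| d8 (dB) | Largest unflagged x (dB) |
|---|---|
| −20 | 23.75 |
| −10 | 21.25 |
| 0 | 18.75 |
| +10 | 16.25 |
| +15 | 15.0 |
| +20 | 13.75 |

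Example: shifts of 20, 20, 20, 15 and 0 dB. Five-frequency mean = 75/5 = 15.0, not flagged. Four-frequency mean = 75/4 = 18.75, which exceeds 15 and falls in the slight band of Table 8.

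**2. Loss at 8000 Hz only.** With x = 0 the shift is d8/5, which exceeds 15 only if d8 > 75 dB. Over 500–4000 Hz the shift would be 0 whatever the size of d8.

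**3. Average air-bone gap.** Let b be the mean bone-conduction shift over 500–4000 Hz. The matched gap shift is x − b. If the average gap were air PTA minus bone PTA, its shift would be (4x + d8)/5 − b, which differs from the matched value by (d8 − x)/5.

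- x = b = 20, d8 = 0: 16 − 20 = −4 dB, although the matched gap shift is 0.
- x = 18.75, d8 = 0: error −3.75 dB.
- x = 0, d8 = 75: error +15 dB.
- All five frequencies shift equally: error 0.

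If the average gap is the mean of the four per-frequency gaps, the error is always 0.

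**4. Different frequencies at the two visits.** Illustration with unchanged hearing: 20 dB at four frequencies and 60 dB at 8000 Hz. With 8000 Hz the PTA is (80 + 60)/5 = 28; without it, 80/4 = 20. Testing 8000 Hz at only one visit gives a false shift of +8 or −8 dB.

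**5. Would a four-frequency PTA plus a separate 8000 Hz count lose anything?** If x ≤ 15 and d8 ≤ 15, then (4x + d8)/5 ≤ (60 + 15)/5 = 15. So, with complete data, every ear the five-frequency mean flags is flagged by at least one of the two rules. The two rules also flag ears that it misses, such as the example in step 1.

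**The case against.** The strongest reply is that the SAP prespecifies a single rule, nothing in the documents requires a 500–4000 Hz average, and including 8000 Hz sometimes helps. Shifts of 15, 15, 15, 15 and 25 dB average 85/5 = 17 over five frequencies and are flagged; over four they average 15 and are not. This is a sound argument against dropping 8000 Hz. It is not an argument against a four-frequency PTA with its own 8000 Hz count, which flags that ear at 25 dB (step 5).

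Several further objections stand and limit the point:

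- A reader might take 18.75 dB as a general limit. It holds only if 8000 Hz does not change.
- A reader might infer that the five-versus-four mismatch is what hides an isolated 8000 Hz loss. It is not. Any average dilutes a single frequency, and a four-frequency PTA alone would never flag such a loss.
- A reader might infer that the average gap will be wrong. The SAP does not say it is a difference of PTAs, and its per-frequency gaps already use matched frequencies.
- A reader might infer that hearing-loss events will be lost. Disagreement with Protocol 12.4 is only possible: no text says investigators use four frequencies. A diagnosed event would still appear in the adverse event tables and listings of SAP 14.1.
- Per-frequency minima and maxima and the subject listings would show extreme ears, though they give no count of ears over the cut-off.
- A fixed four-frequency mean is undefined for ears tested at fewer frequencies, so the fix needs a rule for them.

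**Conclusion.** The point holds in a limited form. On the SAP's own formula, with complete testing, the air-conduction PTA covers five frequencies and the bone-conduction PTA four. The shift table therefore misses a mean 500–4000 Hz worsening above 15 dB and up to (75 − d8)/4 whenever d8 is below 15 dB; the figure is 18.75 dB on the assumption of no change at 8000 Hz.

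Separately, an isolated 8000 Hz loss reaches the table only above 75 dB, as a consequence of averaging. The gap error of (d8 − x)/5 arises if, and only if, the average gap is air PTA minus bone PTA. Because Protocol 12.4 leaves the PTA frequencies unnamed, the adverse event criterion and the table could classify the same ear differently.

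These are descriptive safety outputs. No hypothesis test, primary or secondary, uses them. The change is still worth making because it concerns the cut-off by which ears with worsened hearing are counted.

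**What to change.** In SAP 14.3:

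- Compute air- and bone-conduction PTA over 500, 1000, 2000 and 4000 Hz, the set already used for the per-frequency gap.
- For ears with incomplete testing, including children under 4, use only those of the four frequencies measured at both visits, and report how many were used.
- Define the average air-bone gap as the mean of the per-frequency gaps over the same frequencies.
- Add a by-ear count of 8000 Hz air-conduction worsening above 15 dB. This is essential, not optional, once 8000 Hz leaves the PTA.

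Reconcile Protocol 12.4 with SAP 14.3 so that both cite one PTA definition.

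The cost is wording in two documents and one extra table; no new measurements are needed. Two drawbacks should be accepted openly: a single-frequency count will include some test-retest noise, and PTAs based on few frequencies are less precise.
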